day	Cycle 1			Cycle 2			Cycle 3 and beyond ²					
	1	8	15		1	8	15		1	8	15	
765IGF-MTX*	X	X	X		X	X	X		X	X ¹	X ¹	
Clinic visit	X	X	X		X	X	X		X	X ¹	X ¹	

* at assigned dose level (see table below)

¹Day 8 and day 15 visits at physician's discretion cycle 3 and beyond

²Treatment continues until disease progression, unacceptable toxicity, patient refusal or other reason as found in section 7.11

Phase I Dose Levels

Dose Level	765IGF-MTX Dose	Number of Patients*
1	0.20 µequivalents per kg	1-9
2	0.40 µequivalents per kg	1-9
3	0.80 µequivalents per kg	1-9
4	1.6 µequivalents per kg	1-9
5	2.5 µequivalents per kg	1-9

*dose escalation cohorts between 1-9 patients; total of 9 patients in MTD cohort. At the discretion of the principal investigator, intra-patient dose escalation between cycles is also allowed but only after 2 cycles at the assigned dose level and confirmation of safety in at least 3 patients treated at the higher dose level.

Abbreviations

Abbreviation	Definition
AE	adverse event
ALT	alanine aminotransferase
AML	acute myelogenous leukemia
ANC	absolute neutrophil count
AST	aspartate aminotransferase
BM	bone marrow
CIR	Cumulative Incidence of Relapse rate
cm	centimeter
CR	complete remission
CRI	Compete remission with incomplete hematologic recovery (same as "marrow CR")
CMMI	Chronic myelomonocytic leukemia
CTCAE	(NCI) Common Terminology Criteria for Adverse Events
CTEP	Cancer Therapy Evaluation Program
dL	deciliter
DFS	time to relapse
DLT	dose-limiting toxicity
ECOG	Eastern Cooperative Oncology Group
EGFR	epidermal growth factor receptor
EFS	Event-Free Response
FDA	Food and Drug Administration
h	hour
HL	Hodgkin Lymphoma
IC50	50% Inhibitory Concentration, the concentration needed to inhibit cell growth by 50%
IGF-1	insulin-like growth factor-1
IGF-1R	insulin-like growth factor-1 receptor
IHC	immunohistochemistry
IND	Investigational New Drug
IRB	institutional review board
kg	kilogram
lb	pound
mg	milligram
min	minute
mL	milliliter
mm ³	cubic millimeters
MDS	myelodysplastic syndrome
MTD	maximum tolerated dose
MTX	methotrexate
NCI	National Cancer Institute
O-AML	Oligoblastic acute myelogenous leukemia
ORR	Overall response rate (= CR rate + CRI rate + PR rate)
OS	Overall Survival rate
PK	Pharmacokinetics studies
PD	Pharmacodynamics studies
PFS	Progression free survival (Time to disease progression or death from MDS, O-AML, or CMML)

PO	per os (by mouth)
PR	Partial Remission
RFS	Relapse-Free Survival
SAE	serious adverse event
US	United States

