3.3.4 Plasma 765IGF Level and 765IGF-MTX toxicity/response

3.3.5 Plasma and whole blood IGF-1R level and 765IGF-MTX Toxicity/Response

3.3.6 Assess formation of antibodies against 765IGF-MTX

3.3.7 Assess formation of neutralizing antibodies

3.3.8 IGF-1R expression level in diseased tissue in bone marrow, as measured by IHC, and flow cytometry, and in blood cells as measured by flow cytometry.

4. Overall Design and Study Plan

This pilot study will evaluate the safety and clinical benefit of 765IGF-MTX in patients with advanced, previously treated MDS, CMML or O-AML. 765IGF-MTX is administered as an IV infusion over 1.5 hours on days 1, 8 and 15 of a 28 day cycle. Treatment continues until disease progression, unacceptable toxicity, or patient refusal. Assessment of response will be confirmed with bone marrow studies performed at the end of cycle 2, and every 8 weeks +/- 7 days (2 cycles) thereafter up to the end of cycle 6, and at physician's discretion thereafter.

- Dose Finding Component: Up to 5 dose levels will be tested (refer to schema on page 6). The maximum tolerated dose (MTD) will be determined using the modified toxicity probability interval design with dose limiting toxicity (DLT) estimated at 0.33.

Our modification involves using cohorts of size 1 for the initial doses, which allows rapid escalation through the initial dose levels, and expanding to cohorts of size 3 once any grade 2 or higher toxicity is observed that is considered related to study drug (with the exception of alopecia, nausea, or diarrhea). Additional patient cohorts will not be enrolled until 1 of 1 (with no grade 2 toxicity), 3 of 3, 5 of 6, or 7 of 9 patients at the current dose level complete all planned treatment for cycle 1 (defined as 3 doses of 765IGF-MTX without DLT and are able to start cycle 2 with no more than a 2 week delay. At the discretion of the principal investigator, intra-patient dose escalation between cycles is also allowed but only after 2 cycles at one dose level and confirmation of safety in at least 3 patients treated at the higher dose level.

If none of the dose levels are acceptable at study completion, an optimal dose level will not be identified and the drug does not warrant further investigation.

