- Maximum Tolerated Dose (MTD) Cohort with pharmacokinetics (PKs) and pharmacodynamics (PD): The MTD will be defined as the highest dose associated with DLT in less than 33% of patients treated. Once the MTD is determined, enrollment will continue until 9 patients total are accrued at the MTD. For this group, pharmacokinetics will be performed on at least 3 patients before and for up to 48 hours after drug administration on days 1 and 15 of cycle 1. Pharmacodynamic samples will be assessed on day 1 of cycle 1, and days 1 and 15 of cycle 2 before the infusion of 756IGF-MTX, and one sample will also be drawn within the fourth week of each treatment cycle.

If none of the dose levels are acceptable at study completion, an optimal dose level will not be identified and the drug does not warrant further investigation.

Dose limiting toxicity (DLT) for a patient is defined as one of the following events occurring during cycle 1:

- Grade 4 or greater treatment related hematologic toxicity for > 7 days during the first cycle (28 days) of therapy
- Grade 3 or greater treatment related clinical non-hematological toxicity (excluding \geq grade 3 nausea, vomiting, or diarrhea without maximal medical intervention and/or prophylaxis) during the first cycle (28 days) of therapy
- Febrile neutropenia during the first cycle (28 days) of therapy

- Platelets less than $10 \times 10^9/L$ with clinically significant bleeding during the first cycle (28 days) of therapy

Additional patient cohorts will not be enrolled until 1 of 1 (with no grade 2 toxicity), 3 of 3, 5 of 6, or 7 of 9 patients at the current dose level complete all planned treatment for cycle 1 (defined as 3 doses of 765IGF-MTX without DLT and are able to start cycle 2 with no more than a 2 week delay).

The MTD will be defined as a dose level at which fewer than 33% of patients treated experience a DLT.

A minimum of 9 patients are to be treated at the MTD to assure safety and 765IGF-MTX based pharmacokinetics will be performed on at least 3 patients in total.

Pharmacokinetics will be performed before and for up to 24 hours after drug administration on days 1 (for 24 hrs) and 15 (for 24 hrs) of cycle 1. Pharmacodynamic samples will be assessed pre-dosing on day 1 of cycle 1, pre-dosing on days 1 and 15 of cycle 2, and pre-dosing on day 15 of cycles 4 and 6.

5. Selection of Patients

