7.2. Dose Modifications

7.2.1. Start of a New Cycle

Toxicity and adverse will be classified according to NCI's Common Terminology Criteria for Adverse Events Version 4.0 (CTCAE). A copy of the CTCAE can be downloaded from the CTEP home page:

(http://ctep.cancer.gov/protocolDevelopment/electronic_applications/ctc.htm#ctc_40).

Assessment of clinical benefit will be performed by investigators at the end of cycle 1 and confirmed with bone marrow studies as per MDS, CMML or O-AML specific response criteria (Appendices I and II) done at the end of cycles #2, 4, and 6 (i.e., at 8, 16, and 24 weeks, each +/- 7 days) and at the discretion of the physician thereafter.

A new treatment cycle will only be initiated when all of the following conditions are met:

- non- hematologic treatment related toxicities have improved to \leq Grade 1 (CTCAE v.4.0) or to the patient's baseline values (except alopecia)
- Platelets per 7.1 (platelets $> 10 \times 10^9/L$)

If blood counts are below this threshold at the 4 week point, blood work is to be repeated weekly until counts are at an acceptable level. Treatment will be restarted with appropriate dose modifications provided CTCAE hematologic grade ≥ 4 is not prolonged for more than 6 weeks in the absence of persistent disease. If treatment is unable to restart within 4 weeks of the planned treatment date, the patient will be permanently discontinued from study therapy.

CTCAE v.4.0 Adverse Effects Terms & Descriptions (see below for allergic reaction/hypersensitivity)	765IGF-MTX Dose Modifications (for treatment-related toxicities deemed clinically significant)
Any persistent (>4 weeks) grade 2 treatment-related non-hematologic toxicity	Drop to next lower dose level or discontinue treatment.
Grade 4 or greater treatment-related hematological toxicity for >7 days.	Drop to next lower dose level or discontinue treatment.
Grade 3 or greater treatment-related clinical non-hematological toxicity, excluding grade 3 nausea, vomiting, or diarrhea without maximal medical intervention and/or prophylaxis.	Drop to next lower dose level or discontinue treatment.
Febrile neutropenia.	Drop to next lower dose level or discontinue treatment.
Platelets less than $10 \times 10^9/L$	Wait to improve and then drop to next lower dose level or discontinue treatment.

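### The DLT definition, the dose-modification table and the single-patient escalation gate classify the same nausea, vomiting, diarrhea or grade 2 event differently

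*Combined protocol and SAP*

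**What the plan says.** Section 4 (Overall Design and Study Plan) counts related clinical non-hematological toxicity of grade 3 or more in cycle 1 as a DLT, "excluding \geq grade 3 nausea, vomiting, or diarrhea without maximal medical intervention and/or prophylaxis". The dose-modification table in section 7.2.1 has nearly the same sentence, but its carve-out reads "excluding grade 3 nausea, vomiting, or diarrhea without maximal medical intervention and/or prophylaxis". The action there is a drop of one dose level or discontinuation, for related toxicities deemed clinically significant.

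Section 4 starts with cohorts of one, "expanding to cohorts of size 3 once any grade 2 or higher toxicity is observed that is considered related to study drug". Three kinds of event are carved out of this trigger at any grade: "with the exception of alopecia, nausea, or diarrhea". The next sentence, repeated after the DLT list, sets a condition for enrolling further cohorts: "1 of 1 (with no grade 2 toxicity), 3 of 3, 5 of 6, or 7 of 9 patients at the current dose level" must first get through cycle 1. That means three doses without a DLT and cycle 2 started with at most a two-week delay.

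On the MTD, section 4 says: "The MTD will be defined as a dose level at which fewer than 33% of patients treated experience a DLT". On the size of the cohort at that dose, it asks for more: "A minimum of 9 patients are to be treated at the MTD to assure safety". The footnote to the dose table in the Study Schema agrees: "dose escalation cohorts between 1-9 patients; total of 9 patients in MTD cohort".

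On supportive care, section 7.9 rules out antidiarrheal prophylaxis and directs loperamide from the first loose stool. Section 7.8 withholds antiemetic prophylaxis unless the drug proves to cause acute nausea and vomiting. Section 7.1.1 nevertheless allows optional premedication that includes an antiemetic.

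**The concern.** The DLT count gates escalation and sets the MTD, so two people applying the rules to one patient should reach the same answer. In three places they may not.

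1. One exemption carries two grade limits. A grade 4 gastrointestinal event can be serious enough to lower that patient's dose and still not count as dose-limiting.
2. The exemption refers to absent prophylaxis in a trial that itself withholds prophylaxis for diarrhea.
3. The trigger that enlarges a cohort and the gate that releases the next cohort use different lists of events.

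The events are foreseeable. Section 7.1.1 reports nausea during infusion with this drug (grade not stated), and section 10.1.8 lists diarrhea and vomiting among the delayed toxicities of methotrexate.

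**Working it through.** The plan gives no figure to reproduce: section 13.1 leaves the sample size open and involves no hypothesis test. The check compares the rules and then does the arithmetic of the DLT counts.

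**Step 1. The same event under each rule.** Here, not maximally managed means without maximal medical intervention.

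| Event in a lone patient, cycle 1 | DLT (section 4) | Action (section 7.2.1) | Trigger to cohorts of 3 (section 4) | Single-patient gate, read literally |
|---|---|---|---|---|
| Related grade 2 nausea | No | None unless it persists beyond 4 weeks | No (exempt) | Not met |
| Unrelated grade 2 event | No | None | No (not related) | Not met |
| Related grade 3 hematologic toxicity other than febrile neutropenia | No | None | Yes | Not named (grade 2 only) |
| Related grade 4 diarrhea, not maximally managed | No | Drop or discontinue if clinically significant | No (exempt, no grade cap) | Not named (grade 2 only) |
| Related grade 3 diarrhea, fully treated, no prophylaxis | Depends on reading | Depends on reading | No (exempt) | Depends on the DLT call |

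In the first two rows the trigger leaves the cohort at 1 but the literal gate is not met, and the text gives no next step. The next listed count is 3 of 3, so a cautious reader would add 3 − 1 = 2 patients. A reader who takes the gate as shorthand for the trigger would add none.

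**Step 2. The prophylaxis wording.** Reading A: absence of prophylaxis alone exempts an event. Section 7.9 rules out antidiarrheal prophylaxis for everyone, so every grade 3 or higher diarrhea would be exempt and none could be a DLT. Reading B: only absence of maximal treatment exempts. Treated diarrhea then counts, and exempt events should be uncommon because loperamide starts at the first loose stool. Reading B is more natural, because under A the reference to maximal intervention would do no work for diarrhea. The text does not choose. For nausea and vomiting the difficulty is milder, since section 7.1.1 permits antiemetic premedication.

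**Step 3. DLT counts.** The gates allow 0/1, 0/3, 1/6 = 16.7% and 2/9 = 22.2%, all below 33%. One more DLT gives:

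- 3 patients: 1/3 = 33.3%, gate of 3 of 3 not met; the next listed count is 5 of 6
- 6 patients: 2/6 = 33.3%, gate of 5 of 6 not met; the next listed count is 7 of 9
- 9 patients: 3/9 = 33.3%, fails both 7 of 9 and the MTD definition

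The first two are interim. The decisive case is 2/9 against 3/9, which needs two counted DLTs plus one exempt event among the nine.

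**Step 4. Illustration under assumed rates.** The documents give no rate for severe gastrointestinal events. Suppose the DLT rate including all of them is 0.33, with nine independent patients. The binomial chance of at most 2 DLTs is then 0.385. If 5, 10 or 15 percentage points of that rate are exempt, the counted rates are 0.28, 0.23 and 0.18, and the chance becomes 0.517, 0.657 or 0.790. This covers the whole exempt class; the part due to grade 4 alone would be smaller. The conclusion does not rest on these rates.

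**The case against.** The best case for the plan has four parts.

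- DLT and dose-modification lists need not match item by item, and section 7.2.1 might have lost a greater-than-or-equal sign in text extraction. This stands in part. If the sign was there, the mismatch between the two sections disappears, but the DLT exemption still has no upper grade. Other such symbols in section 7.2.1 survived.
- The gate sentence directly follows the trigger in section 4, so shorthand is a natural reading, and the literal reading errs on the cautious side. Both remarks are fair. Yet the gate is repeated after the DLT list without the qualifiers, and nothing says that they carry over.
- Exempting undertreated grade 3 gastrointestinal events is a reasonable choice. Agreed, and the fix keeps it.
- Other provisions protect patients. Section 10.1.9 requires therapy to be interrupted for diarrhea, sections 7.1 and 7.2.1 require related non-hematologic toxicity to recover to grade 1 (7.2.1 also accepts baseline) before a new cycle, and section 11.2 has the investigator or treating physician told of grade 2 or higher toxicity the same day. The gate sets a minimum condition and does not order escalation.

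A reader might infer that a lone patient with grade 4 diarrhea would send the next patient straight to a higher dose. The documents do not support that as a likely path. It needs the shorthand reading of the gate, an event not maximally managed despite section 7.9, all three doses given despite section 10.1.9, recovery, and a timely cycle 2. Section 10.1.8 also does not list diarrhea among the other events observed with this drug; it appears there as a methotrexate toxicity.

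**Conclusion.** The rules conflict in three places: the grade limit of the gastrointestinal exemption, the effect of absent prophylaxis, and the mismatch between trigger and gate. For the events in the table they can give opposite DLT or cohort-size decisions, which is more than missing detail.

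The practical effect is limited. For the final MTD, one exempt event is decisive only when two other DLTs have occurred among nine patients. For the gate, the readings differ by 2 patients at a level.

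Two stronger conclusions would go too far. Severe nausea, vomiting and diarrhea are not excluded from the DLT definition altogether: on the more natural reading, events despite maximal management count. Nor are exempt events lost to the safety analysis: section 11.2 requires all grades on internal forms, and section 13.3 reports graded toxicity, delays and dose reductions. They would be missing only from the DLT count.

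The grade-limit part assumes that section 7.2.1 reads as extracted; the other two do not depend on it.

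**What to change.** - Limit the DLT exemption in section 4 to grade 3 nausea, vomiting or diarrhea that was not given maximal medical treatment, so that any related grade 4 event is a DLT.
- Delete the reference to prophylaxis, or state that lack of prophylaxis the protocol itself withholds does not exempt a treated event.
- Cap the trigger's exemption for nausea and diarrhea at grade 2.
- Restate the single-patient gate, in both places, as no related toxicity of grade 2 or higher, with the same exemptions as the cohort-size trigger.

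This changes protocol wording only. It costs up to 2 more patients at a level where a lone patient has related grade 3 or higher nausea or diarrhea. The gate also becomes slightly looser than its literal text for exempt or unrelated grade 2 events, and the sponsor should accept that knowingly.

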6.2. Registered/Enrolled Patients Who Do Not Begin Study Treatment

If a patient signs the informed consent document, is subsequently registered/enrolled to the study but is then not able to begin the planned study treatment for any reason, the patient will be removed from study and treated at the physician's discretion. The patient will be considered a screen/baseline failure and be replaced. Further data will not be collected if the patient has not begun study treatment at the time of removal from trial. The reason for removal from study will be clearly indicated in EDC Easy®.

If a patient begins treatment and is then removed from treatment for any reason, the patient must be followed per section 7.11.

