7.10. Duration of Therapy

Patients will receive protocol therapy unless:

- Extraordinary Medical Circumstances: If at any time the constraints of this protocol are detrimental to the patient's health, protocol treatment should be discontinued.
- Patient withdraws consent.
- There is evidence of progressive disease or unacceptable toxicity.
- The treating physician thinks a change of therapy would be in the best interest of the patient.
- More than a 4 week delay between cycles

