7.11. Follow-up

Administration of study medication will be continued after cycle 2 until disease progression, unacceptable toxicity, or patient withdrawal. A final study visit will occur 30 days (+/-1 week) after the last dose of 765IGF-MTX. This visit will end study participation unless there is ongoing toxicity at least possibly related to study treatment. In this case, the patient will be followed as medically appropriate until resolution or stabilization of the adverse event.

8. Study Parameters

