11.2. Adverse Event Documentation

Adverse events occurring from the first dose of 765IGF-MTX up to and including 30 days after administration of the last dose must be documented. Adverse events attributed to a study-related procedure which occur prior to the initiation of study treatment must be documented as well.

For the purposes of this study, adverse event documentation requirements will be determined based on grade, expectedness and relationship to study therapy as follows:

	Grade 1	Grade 2		Grade 3		Grade 4 and 5
	Expected or Unexpected	Expected	Un-expected	Expected	Un-expected	Expected or Unexpected
Unrelated	Not required	Not required	Not required	Not required	Required	Required

Possible						
Probable						
Definite	Not required	Required	Required	Required	Required	Required

All patients will be monitored with appropriate event documentation in EDC Easy® through the final study visit per section 7 as it is expected that most treatment related adverse events will occur during this period.

However, all toxicities (grades 1, 2, 3, 4, 5) must be reported within internal study forms, and include the following descriptors:

- Toxicity
- Grade
- Date
- Expected or Unexpected
- Attribution (unrelated, unlikely, possible, probably, definite)

For grade 2 or higher toxicities, principal investigator and/or treating physician will be notified the same day as study visit.

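### Section 4's escalation gate counts a non-toxic early exit as a failure and no rule replaces that patient, so escalation can stop at a tolerable dose

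*Combined protocol and SAP*

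**What the plan says.** Section 4 (Overall Design and Study Plan) sets two rules on the same patients.

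- **Escalation gate.** Further cohorts wait until 1 of 1 (with no grade 2 toxicity), 3 of 3, 5 of 6 or 7 of 9 patients at the current level "complete all planned treatment for cycle 1 (defined as 3 doses of 765IGF-MTX without DLT" and can begin cycle 2 after a delay of at most two weeks.
- **MTD rule.** "The MTD will be defined as a dose level at which fewer than 33% of patients treated experience a DLT". The DLT list in Section 4 contains only toxicity events in cycle 1.

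Single-patient cohorts are enlarged by "expanding to cohorts of size 3 once any grade 2 or higher toxicity is observed that is considered related to study drug", with a few listed exceptions. No other trigger is given.

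Section 7.10 foresees stopping for reasons other than toxicity, among them withdrawal of consent, progression and this one: "The treating physician thinks a change of therapy would be in the best interest of the patient".

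Section 6.2 provides replacement only for a registered patient who never begins treatment: "The patient will be considered a screen/baseline failure and be replaced". For the others it says: "If a patient begins treatment and is then removed from treatment for any reason, the patient must be followed per section 7.11". Section 7.11 then specifies the follow-up: "A final study visit will occur 30 days (+/-1 week) after the last dose of 765IGF-MTX". No DLT-evaluable population is defined in Sections 4, 6.2, 7.10, 7.11 or 13.

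**The concern.** A patient who receives one dose and then leaves for a reason unrelated to toxicity is a non-completer for the gate. The gate tolerates no non-completer at one or three patients, one at six and two at nine, so each such exit uses room that would otherwise absorb a DLT.

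At the single-patient stage the position is worse. The exit fails 1 of 1 and rules out 3 of 3. The next pass point still within reach is 5 of 6, which needs five more completers. The only stated trigger for enlarging the cohort is related toxicity, so the text does not tell the site what to do.

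Determining the MTD is part of the primary objective (Section 2.1). If escalation stops because patients left rather than because they were harmed, the dose taken forward may be too low. The Study Schema limits each level to 1-9 patients, so exits cannot simply be outnumbered by further enrolment.

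**Working it through.** **Step 1: the plan's own counts.** The largest DLT count x with x/n below 0.33 is 0, 0, 1, 2 at n = 1, 3, 6, 9, since 1/3, 2/6 and 3/9 are all 33.3%. The gate allows 1−1, 3−3, 6−5, 9−7 = 0, 0, 1, 2 non-completers. The two rules agree exactly when every non-completer is a DLT. Only other kinds of non-completion separate them.

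**Step 2: example.** With nine treated, no DLTs and three non-toxic exits, the DLT rate is 0/9 = 0% but completers are 6 of 9, and the gate fails. This exact outcome, with the gate not passed earlier, is uncommon: 1.6% at 10% exits and 6.1% at 20% (true DLT rate 10%, leavers at no DLT risk).

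**Step 3: gate.** The gate counts come from Section 4. The documents give neither a DLT rate nor an exit rate, so I assume a true DLT rate of 0.10 and a non-toxic exit rate d of 0 to 0.20. Cohorts of three are used throughout, the gate is the only escalation rule, and DLTs and non-toxic exits are the only causes of non-completion.

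Per-patient completion is q = 0.90(1−d), and failure is f = 1−q. The chances of clearing are:

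- at 3: q³
- first at 6 (one failure, in the first three): 3fq⁵
- first at 9 (two failures by six, at least one in the first three, none after): (9+3)f²q⁷ = 12f²q⁷

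| d | f | at 3 | at 6 | at 9 | cleared by 9 | uncleared, toxicity acceptable |
|---|---|---|---|---|---|---|
| 0 | 0.100 | 0.729 | 0.177 | 0.057 | 0.964 | 0 |
| 0.02 | 0.118 | 0.686 | 0.189 | 0.069 | 0.944 | 0.020 |
| 0.05 | 0.145 | 0.625 | 0.199 | 0.084 | 0.908 | 0.057 |
| 0.10 | 0.190 | 0.531 | 0.199 | 0.099 | 0.829 | 0.134 |
| 0.20 | 0.280 | 0.373 | 0.163 | 0.094 | 0.630 | 0.321 |

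The last column sums the uncleared paths at nine patients with two or fewer DLTs and DLTs/(9 − exits without DLT) below 0.33. Leavers there carry no DLT risk. If they keep half of it, the last two entries become 0.130 and 0.311.

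**Step 4: MTD rate (secondary).** The early leaver without a DLT stays among patients treated as DLT-free. With 2 DLTs in 9, removing 0, 1, 2 or 3 leavers gives 2/9, 2/8, 2/7, 2/6 = 22.2, 25.0, 28.6, 33.3%. The verdict changes only at three exits, or in rarer cases with fewer DLTs and more exits (1 DLT and 6 exits: 1/3).

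Take a true DLT rate of 0.40, fixed n = 9 and leavers at no risk. At d = 0.20 the per-patient chances are 0.40×0.80 = 0.32 (DLT), 0.20 (exit) and 0.48 (completer). The main term, 2 DLTs and 3 exits, is 1260 × 0.32² × 0.20³ × 0.48⁴ = 0.055. All flip cases sum to 0.086. If leavers keep half the risk, the sum is 0.050. At d = 0.10 the range is 0.009 to 0.017, and at d = 0.05 it is at most 0.003.

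**Step 5: after the change.** With replacement the gate clears with chance 0.964 if leavers carry no risk. At half risk it is 0.959 and 0.952 for d = 0.10 and 0.20. Expected replacements per nine evaluable patients are 9d/(1−d) = 0.47, 1.0 and 2.25 at d = 0.05, 0.10 and 0.20.

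**The case against.** **The strictness may be deliberate.** The primary objective covers tolerability as well as safety, and Section 13.3 bases tolerance on delays and dose reductions as well as DLTs. A gate requiring full treatment and a timely cycle 2 fits that aim and errs on the safe side. This stands for toxicity-related non-completion, and the change below keeps it. It gives no reason to count a patient who left for an unrelated reason.

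**The exit rates are assumed and may be low.** The last cycle 1 dose is on day 15, and the synopsis assesses progression after two cycles. This stands. At 2% or 5% exits the gate still clears with chance 94% or 91%, so the loss is small.

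**The gate may not be the whole algorithm.** Section 4 names mTPI with a target of 0.33 and does not say how it combines with the completion counts. This stands as a limit on the figures.

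**The full SAP may settle it.** Section 13 promises one, finalised before database lock. It could define the MTD denominator, but escalation decisions are taken earlier, so it cannot supply the replacement rule.

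**A stronger reading is tempting:** that early leavers go unobserved and so let a toxic dose be named the MTD. The documents do not support this. Section 11.2 says: "Adverse events occurring from the first dose of 765IGF-MTX up to and including 30 days after administration of the last dose must be documented". Unless consent is withdrawn, what is lost is mainly exposure to later doses. One or two exits cannot change the verdict at nine patients, and Step 4 conditions on reaching nine patients at a dose with a 40% DLT rate, so it is not the trial's overall chance of naming a toxic dose.

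**Conclusion.** The point holds for the gate. As written, non-toxic exits count against escalation, nobody replaces those patients, and the MTD can be set too low for reasons unrelated to toxicity. At a true DLT rate of 10%, the chance that the gate stays shut despite acceptable toxicity is about 2% at 2% exits, 6% at 5%, 13% at 10% and 32% at 20%. These figures rest on assumed rates and on reading the gate as binding alongside mTPI.

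The error is conservative, and a level that fails the gate can still be named MTD, so a reader should not infer a threat to patient safety. Dilution of the MTD rate is a secondary note: at a true DLT rate of 40% it changes the verdict with chance at most 0.3% at 5% exits, 0.9-1.7% at 10% and 5.0-8.6% at 20%. The change should be made because it is cheap and the rule is needed while the trial is running.

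**What to change.** In Section 4, define a DLT-evaluable patient as one who meets any of these conditions:

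- had a DLT
- received all three cycle 1 doses and was observed through day 28
- missed or stopped doses because of toxicity that is treatment-related or of uncertain cause

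Replace every treated patient outside this set, whether the patient left the study or only missed a dose for a clearly non-toxic reason. Apply this at the single-patient stage too. Use the set for both the gate and the MTD rate. Count failure to start cycle 2 within two weeks against the gate only when it is due to toxicity or its cause is uncertain. State that replacements do not count toward the 1-9 limit per level, and keep all treated patients in the safety tables.

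The gate then remains stricter than the MTD rate for toxicity below DLT grade that prevents completion.

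The cost is protocol wording, an attribution judgment for each exit, and about 0.5, 1 or 2 replacements per nine evaluable patients at 5%, 10% or 20% exits. Attribution is hard in refractory, cytopenic patients, and a wrong call would remove a cautionary case. The default in doubt should therefore be to treat the patient as evaluable.
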